7. STUDY TREATMENT

7.1. Investigational Product and Other Study Treatment

Investigational product in this study is defined as RVT-101 tablets and will be provided by Axovant Sciences. Investigational product will be supplied as single individual bottles, each bottle containing 50 tablets. One bottle of investigational product will be supplied at each of Visits 1, 2, and 3; two bottles will be dispensed at each of Visits 4, 5, and 6. This will be sufficient investigational product to cover the interval between visits, including the protocol-allowed visit window, plus some overage.

Donepezil and other background therapies will be clinically prescribed by the Investigator or treating physician and will not be supplied by the sponsor.

Characteristic	Investigational Product
Product Name:	RVT-101
Formulation Description:	Pink film-coated round tablets
Dosage Form:	35-mg tablet
Unit Dose Strength(s)/ Dosage Level(s):	35 mg/ 35 mg
Route of Administration: Duration (Treatment Period):	Oral 52 weeks
Dosing Instructions:	Take 1 tablet orally each morning without regard to food
Manufacturer/Source of Procurement	Catalent Pharma Solutions, Kansas City, MO USA

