7.6. Compliance with Investigational Product Administration

Every effort should be made to encourage subject compliance with the dosage regimen as per protocol for investigational product. The investigator is responsible for discussing with subjects methods to ensure high treatment compliance. All subjects should be instructed to return investigational product bottles with any unused drug at each visit to the investigator. A record of the supplies dispensed, taken, and returned at each visit will be made in the source documents and eCRF. For each bottle, the investigator or designee is responsible for reconciling the number of tablets returned with the expected number of tablets taken and accounting for any discrepancies.

Subjects should be withdrawn from the study if they have demonstrated significant non-compliance with investigational product administration without acceptable explanation, in the opinion of the Investigator and after discussion with the Medical Monitor. While interruptions in investigational product administration should be avoided wherever possible, short-term interruptions due to forgetfulness; caregiver illness or absence; a pause in investigational product administration required during an intervention, hospitalization, or while a subject considers the study continuation; or for any other reason are not grounds for automatic withdrawal but should be assessed by the investigator.

Other major protocol violations as well as use of prohibited drugs (see Section 7.9.2) may be cause for discontinuation of investigational product or withdrawal from the study.

Decisions regarding dose interruptions will be made by the investigator in consultation with the Medical Monitor based on the clinical evaluation of the subject.

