Open-Label Treatment Period (V2 through V7): Visits 2 through 7 should be scheduled relative to V1 with a visit window of ± 7 days. If the visit window is used, the subsequent visit should remain according to the planned visit schedule (i.e., the subsequent visit date should not be re-calculated from the date of the previous visit but should remain relative to baseline).

Investigational product compliance will be performed on returned study bottles, and new bottles of investigational product will be dispensed, at each visit. Subjects will be reminded to take the investigational product once daily in the morning with or without food.

Subjects who prematurely discontinue from the open-label treatment period will be required to attend a safety clinic visit, preferably within 7 days of stopping the investigational product, and perform the procedures indicated for the V7/Early Termination (ET) Visit.

Follow-Up Visit (V8): All subjects who complete the open-label treatment period will be contacted by phone 14 to 19 days after the last dose of investigational product is taken to assess for any new AEs and follow-up on any open AEs. The Investigator may choose to conduct this visit in the clinic and may perform additional assessments if results of any of the V7 evaluations are considered clinically significant.

Table 2. Time and Events Schedule

Study Period:	Screening and Baseline	Open-Label Treatment Period										Follow-up	Unscheduled ^b	
		V1 ^a	V2	V3	V4	V5	V6	V7/ET	V8					
Study Visit Number:	W0	W4	W10	W16	W28	W40	W52	W54						
Study Day: relative to Baseline unless specified	0	28 ± 7	70 ± 7	112 ± 7	196 ± 7	280 ± 7	364 ± 7	14 to 19 days after last dose of IP						
Informed consent	X													
Inclusion and exclusion criteria	X													
Demography, standard medical history	X ^e													
Targeted medical history ^d	X													
Prescription for donepezil ^e	X													
Concomitant medications review	X ^e	X	X	X	X	X	X	X	X	X	X	X	X	X
Urine Drug screen	X											X ^f		X
C-SSRS	X	X	X	X	X	X	X	X	X	X	X	X	X	X
Dispense IP	X	X	X	X	X	X	X	X	X	X	X	X	X	X
Assess IP compliance		X	X	X	X	X	X	X	X	X	X	X	X	X
Physical exam	X			X			X					X		X
Neurological exam	X			X			X					X		X
12-lead ECG	X			X			X					X		X
Vital signs ^g	X	X	X	X	X	X	X	X	X	X	X	X	X	X
Review AEs		X	X	X	X	X	X	X	X	X	X	X	X	X

Study Period:	Screening and Baseline	Open-Label Treatment Period								Follow-up	Unscheduled ^b
		V1 ^a	V2	V3	V4	V5	V6	V7/ET	V8		

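### One 50-tablet bottle at Visits 2 and 3 can fall up to 6 days short of an in-window visit interval, contrary to the supply statement in section 7.1

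*Combined protocol and SAP*

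**What the plan says.** Section 7.1 of the protocol describes the product as supplied in bottles, "each bottle containing 50 tablets", taken as one tablet each morning. It continues: "One bottle of investigational product will be supplied at each of Visits 1, 2, and 3", with two bottles at each of Visits 4, 5 and 6. It then concludes: "This will be sufficient investigational product to cover the interval between visits, including the protocol-allowed visit window, plus some overage".

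Section 8.1 sets the timing: "Visits 2 through 7 should be scheduled relative to V1 with a visit window of ± 7 days". If a window is used, "the subsequent visit date should not be re-calculated from the date of the previous visit but should remain relative to baseline". Table 2 puts Visits 2, 3 and 4 at days 28, 70 and 112, each with ±7 days.

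On leftover tablets, section 7.6 says: "All subjects should be instructed to return investigational product bottles with any unused drug at each visit to the investigator". Section 8.1 says that "new bottles of investigational product will be dispensed, at each visit". Section 7.5 has unused product reconciled and sent back when the sponsor asks for it. No section says that counted tablets are given back to the subject, and none forbids it.

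**The concern.** Because every window is anchored to Visit 1, an early visit followed by a late one lengthens the interval between them by both deviations. The statement in section 7.1 appears to allow for only one. For the two six-week intervals, a single bottle leaves one tablet to spare if one window is counted and too few if both are.

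A subject who attends every visit in window and takes every dose could therefore run out of tablets. Section 7.6 asks that interruptions be avoided where possible, yet here the supply rule itself could cause one. The subject would have slightly less exposure than planned, and the site would have to explain a tablet count that does not match the days elapsed. A site relying on section 7.1 would have no reason to expect this.

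**Working it through.** **Inputs.** Tablets per bottle: 50. Bottles: 1 at each of Visits 1 to 3, 2 at each of Visits 4 to 6. Dose: 1 tablet a day (all section 7.1). Visit days: 0, 28, 70, 112, 196, 280, 364, with ±7 days from Visit 2 to Visit 7 (Table 2), anchored to Visit 1 (section 8.1).

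**The plan's own statement, with the window counted once.** For Visits 2–3 and 3–4: 42 + 7 = 49 days against 50 tablets, 1 to spare. On this reading the statement holds.

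**Both windows counted, as section 8.1 permits.** Longest interval = (later visit day + 7) − (earlier visit day − 7), with Visit 1 fixed at day 0.

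| Interval | Longest interval (days) | Tablets | Margin |
|---|---|---|---|
| V1–V2 | 35 − 0 = 35 | 50 | +15 |
| V2–V3 | 77 − 21 = 56 | 50 | **−6** |
| V3–V4 | 119 − 63 = 56 | 50 | **−6** |
| V4–V5 | 203 − 105 = 98 | 100 | +2 |
| V5–V6 | 287 − 189 = 98 | 100 | +2 |
| V6–V7 | 371 − 273 = 98 | 100 | +2 |

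Only the single bottles given at Visits 2 and 3 fail.

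**When the shortfall occurs.** Let *e* and *l* be the deviations in days of the earlier and later visit, each from −7 to +7. The interval is 42 + *l* − *e*. It exceeds 50 when *l* − *e* ≥ 9, so the earlier visit must be at least 2 days early and the later at least 2 days late. Of the 15 × 15 = 225 allowed pairs, the number short by 1, 2, 3, 4, 5 and 6 days is 6, 5, 4, 3, 2 and 1, which is 21 pairs. The shortfalls total 6 + 10 + 12 + 12 + 10 + 6 = 56 days, a mean of 56/21 = 2.7 days. This counts schedules. It is not a probability, because the protocol gives no distribution of visit days.

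**Both intervals in one subject.** A short V2–V3 interval needs Visit 3 at least 2 days late; a short V3–V4 interval needs it at least 2 days early. Both cannot hold, so at most one interval per subject is affected.

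**If leftovers are kept.** Cumulative tablets less the latest day: Visit 2, 50 − 35 = +15; Visit 3, 100 − 77 = +23; Visit 4, 150 − 119 = +31. There is then no shortfall.

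**The case against.** The strongest reply is that the shortage depends on a handling rule the protocol never states. The return of bottles in section 7.6 serves the compliance count. Section 7.5 sends unused product to the sponsor only on notification, and section 11.1.7 speaks of return at the end of the study. Neither requires the subject to give up leftovers at each visit. If leftovers are kept, a subject seen on day 21 still has 50 − 21 = 29 tablets, so 79 are available for the next 56 days. This point stands as a condition on the finding. But the text as written has bottles brought back and new ones issued, and a site could reasonably follow it without handing anything back.

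Second, section 8.1 directs the site back to the planned schedule after a window is used. If Visit 2 is on day 21 and Visit 3 on its planned day 70, the interval is 49 days and one bottle suffices. That may be how the supply was calculated. It does not cancel the ±7 days that Table 2 prints for Visit 3, so 56 days remains permitted.

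Third, a site could resupply at an unscheduled visit. Table 2 leaves such visits to the investigator's discretion, and a site that trusts section 7.1 has nothing to prompt one.

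Finally, the consequence is small, and this is accepted. The study is open-label and descriptive, with no hypotheses. Section 7.6 says that short interruptions "or for any other reason are not grounds for automatic withdrawal but should be assessed by the investigator". Tolerability is judged by discontinuations due to adverse events, so a supply gap neither forces withdrawal nor by itself distorts that measure.

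**Conclusion.** The concern holds. The sufficiency statement in section 7.1 is wrong for the bottles dispensed at Visits 2 and 3 under the protocol's own visit rules. The shortfall is 1 to 6 days; the maximum is 6/364 = 1.6% of the treatment period, and no subject can meet it in more than one interval. The conclusion assumes one tablet every day, visits anywhere within the printed windows, and leftovers not handed back; if they are handed back, the shortfall disappears. How many subjects would be affected cannot be estimated from the protocol. The case for a correction is that the stated cover does not exist as written and the dosing gap is easily avoided; no analysis or safety conclusion is threatened.

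**What to change.** Choose one of two changes and reword the sufficiency sentence in section 7.1 to match.

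- **Hand back leftovers (preferred).** State in sections 7.1 and 7.6 that, once counted, unused tablets are returned to the subject along with the new bottle. This needs no extra drug and adds some accountability work at sites.
- **Two bottles at Visits 2 and 3.** This gives 100 tablets for at most 56 days, a margin of +44. The planned supply per completer is 3 × 50 + 3 × 100 = 450 tablets, so the extra 100 tablets add 100/450 = 22%.

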7.2. Randomization/Treatment Assignment

This is an open-label study and no randomization of treatment assignment will occur. Subjects who are enrolled in this study will receive RVT-101 35-mg tablets.

7.3. Blinding

This is an open-label study; no blinding of treatments will occur.

7.4. Packaging and Labeling

RVT-101 35-mg tablets will be packaged in 50-count, high-density polyethylene bottles. Labels for RVT-101 bottles will meet all applicable requirements of the US Food and Drug Administration (FDA), EU Commission Directive 2003/94/EC, Eudralex Volume 10 ANNEX

13-Good Manufacturing Practice for the manufacture of investigational medicinal products (July 2010), and/or other local regulations as applicable.

The label for the investigational product will contain at a minimum the following information for the US (additional items may be added as required for other countries):

- Protocol number
- Lot number
- Bottle identification number
- Quantity
- Dosing directions
- “Caution: New Drug – Limited by Federal law to investigational use. Keep out of reach of children.”

7.5. Preparation/Handling/Storage/Accountability

No special preparation of investigational product is required. Investigational product will be stored at room temperature (15- 30°C) and protected from light.

- Only subjects enrolled in the study may receive investigational product and only authorized site staff may supply or administer investigational product. All investigational product must be stored in a secure, environmentally controlled and monitored (manual or automated) area in accordance with the labelled storage conditions, with access limited to the investigator and authorized site staff.
- The investigator, institution, or the head of the medical institution (where applicable), is responsible for investigational product accountability, reconciliation, and record maintenance (i.e., receipt, reconciliation, and final disposition records).
- Site staff will record the subject number on the packaging label for the investigational product for each bottle dispensed.
- Under normal conditions of handling and administration, investigational product is not expected to pose significant safety risks to site staff. In the case of unintentional occupational exposure, notify the Medical Monitor and/or the Axovant Sciences study contact.
- A Material Safety Data Sheet/equivalent document describing occupational hazards and recommended handling precautions will be provided to the investigator where this is required by local laws, or will be available upon request from Axovant Sciences.
- Unused investigational product will be reconciled and returned to the sponsor upon notification by the sponsor or sponsor representative. The instructions and address for returning unused investigational product will be provided in a separate document.

7.6. Compliance with Investigational Product Administration

Every effort should be made to encourage subject compliance with the dosage regimen as per protocol for investigational product. The investigator is responsible for discussing with subjects methods to ensure high treatment compliance. All subjects should be instructed to return investigational product bottles with any unused drug at each visit to the investigator. A record of the supplies dispensed, taken, and returned at each visit will be made in the source documents and eCRF. For each bottle, the investigator or designee is responsible for reconciling the number of tablets returned with the expected number of tablets taken and accounting for any discrepancies.

Subjects should be withdrawn from the study if they have demonstrated significant non-compliance with investigational product administration without acceptable explanation, in the opinion of the Investigator and after discussion with the Medical Monitor. While interruptions in investigational product administration should be avoided wherever possible, short-term interruptions due to forgetfulness; caregiver illness or absence; a pause in investigational product administration required during an intervention, hospitalization, or while a subject considers the study continuation; or for any other reason are not grounds for automatic withdrawal but should be assessed by the investigator.

Other major protocol violations as well as use of prohibited drugs (see Section 7.9.2) may be cause for discontinuation of investigational product or withdrawal from the study.

Decisions regarding dose interruptions will be made by the investigator in consultation with the Medical Monitor based on the clinical evaluation of the subject.

7.7. Treatment of Investigational Product Overdose

Any dose of RVT-101 greater than 100 mg within a 24-hour time period will be considered an overdose.

No data are available with regard to overdose of RVT-101 in humans. There is no specific treatment to be used in the event of overdose with RVT-101. Investigators should use their clinical judgment in treating cases of overdose as dictated by the subject's clinical status.

In the event of an overdose the investigator or treating physician should:

- Contact the Medical Monitor immediately,
- Closely monitor the subject for AEs/SAEs and laboratory abnormalities and ensure appropriate clinical management. Overdose in the absence of other AEs will not be reported as an AE in its own right.
- Document the quantity of the excess dose as well as the time of administration of the overdose in the eCRF.

7.8. Treatment after the End of the Study

The investigator is responsible for ensuring that consideration has been given to the post-study care of the subject's medical condition.

7.9. Concomitant Medications and Non-Drug Therapies

7.9.1. Permitted Medications and Non-Drug Therapies

All current concomitant medications, including over-the-counter and herbal remedies, will be recorded in the eCRF. Current non-medication therapies related to the subject's AD (neurostimulation, cognitive rehabilitation) must also be recorded. Changes to concomitant medications or non-medication therapies throughout the study must also be recorded. The name of the drug, the dose, indication and route of administration as well as the dates administered should be documented; the minimum requirement is to record the drug name and dates of administration. Any medication not specified in the list of prohibited medications provided in [Table 1](#) is permitted during the study.

Subjects will be required to remain on donepezil at their current stable dose for at least the first 4 weeks of this study; changes in donepezil dose and/or use of alternate background therapy during the first 4 weeks may be made only after approval by the Medical Monitor. After V2, a change in subject's dose of donepezil or transition to another background therapy will be acceptable if clinically warranted. RVT101 efficacy has been demonstrated in a previous study as an adjunctive therapy to donepezil and it is recommended that subjects remain on donepezil therapy throughout the course of the study. However, if the investigator or treating physician determines that a change in type or dose of background therapy is warranted after Visit 2, it will not be considered a protocol violation and subjects do not need to be discontinued from the study. Donepezil and other background therapies will be clinically prescribed by the Investigator or treating physician and will not be supplied by the sponsor. The background therapy name, dose, route of administration, administration dates, and any changes should be recorded in the concomitant medication eCRF.

Subjects may begin to concomitantly use memantine or other medications used to treat dementia or other cognitive impairments after Visit 2, as long as the medication is not specified in the list of prohibited medications provided in [Table 1](#). The use of memantine (including dose, administration dates, and any changes) should be recorded in the concomitant medication eCRF.

7.9.2. Prohibited Medications and Non-Drug Therapies

Subjects who take any prohibited medication during the study should be withdrawn from the study. However, in some situations in which a prohibited medication is required for a limited period of time, investigational product may be discontinued during the treatment of the prohibited medication and restarted after the termination of the prohibited medication, if considered appropriate by the investigator and with prior discussion with the Medical Monitor, based on subject safety and the perceived need for the prohibited treatment. Use of prohibited

medications must be documented in the Concomitant Medications section of the eCRF. Prohibited medications are listed in [Table 1](#).

Table 1. List of Prohibited Medications

Prohibited Medications: Not allowed during the study or within 5 half-lives prior to V1/Screening

 • Selegiline • Butyrophenones, phenothiazines, and other “conventional” antipsychotics • Barbiturates • MAO inhibitors • Any investigational drug • Substrates of CYP2C9¹ with narrow therapeutic indices: warfarin, phenytoin and (R)-acenocoumarol (active component of some non-warfarin anticoagulants) • Potent CYP3A4² inhibitors/inducers such as ketoconazole, itraconazole, erythromycin, rifampicin, phenytoin and carbamazepine • Known potent P-gp inhibitors³ (itraconazole, ketoconazole, cyclosporin, diltiazem, verapamil, quinidine, and carvedilol)

Abbreviations: MAO = monoamine oxidase; Pgp = permeability glycoprotein

Notes:

¹RVT-101 affects CYP2C9 substrates.

²CYP3A4 is a major enzyme involved with the metabolism of RVT-101.

³Pgp inhibition may affect CNS levels of RVT-101.

7.10. Lifestyle and/or Dietary Restrictions

7.10.1. Meals and Dietary Restrictions

Subjects should refrain from consumption of grapefruit or grapefruit juice due to the potential to raise RVT-101 concentrations.

8. STUDY ASSESSMENTS AND PROCEDURES

Protocol waivers or exemptions are not allowed, with the exception of immediate safety concerns. Therefore, adherence to the study design requirements, including those specified in the Time and Events Table, are essential and required for study conduct.

8.1. Time and Events

The Time and Events Schedule ([Table 2](#)) displays each study assessment and procedure along with the time of occurrence. V1 of this study may be combined with the final on-treatment visit, V8, of lead-in study RVT-101-3001, or be conducted within 4 weeks of that visit. V2 will occur approximately 4 weeks after V1; V3 and V4 will each occur approximately 6 weeks after the previous visit; subsequent visits will occur approximately every 3 months thereafter. In the event of spontaneously reported tolerability problems, an unscheduled visit will be arranged to assess the subject.

All study assessments should be conducted by the investigator, and/or a suitably qualified designee approved and documented for this study. Information for each visit will be recorded in the source documents and, where appropriate, the eCRF.

V1/Screening/Baseline: The final on-treatment visit, V8, of lead-in study RVT-101-3001 may serve as V1 of this study. If V1 of this study occurs at the same time or within 7 days of V8 of the lead-in study RVT-101-3001, then the procedures conducted for V8 of the lead-in study RVT-101-3001 may serve as the procedures required for V1 of this study and need not be repeated. If V1 of this study occurs greater than 7 days after V8 of the lead-in study RVT-101-3001, then all procedures specified for V1 of this study must be repeated and cannot be combined with the procedures performed on V8 of the lead-in study RVT-101-3001. V1 of this study must occur within 4 weeks of V8 of the lead-in study.

An ICF will be signed by each subject, if he or she is able, or by the subject's legally authorized representative with subject assent before any study-specific procedures are performed. An ICF will also be signed by the caregiver before any study-specific procedures are performed. Subjects will be screened for eligibility according to study inclusion/exclusion criteria at this visit. Eligible subjects will be dispensed investigational product and will be instructed to take it once daily in the morning with or without food.

Subjects who do not qualify for the study during this visit will be considered Screen Failures, and may be rescreened (only once) after discussion with the Medical Monitor. The repeat screening visit must occur within 4 weeks of the original screening visit.

Open-Label Treatment Period (V2 through V7): Visits 2 through 7 should be scheduled relative to V1 with a visit window of ± 7 days. If the visit window is used, the subsequent visit should remain according to the planned visit schedule (i.e., the subsequent visit date should not be re-calculated from the date of the previous visit but should remain relative to baseline).

Investigational product compliance will be performed on returned study bottles, and new bottles of investigational product will be dispensed, at each visit. Subjects will be reminded to take the investigational product once daily in the morning with or without food.

Subjects who prematurely discontinue from the open-label treatment period will be required to attend a safety clinic visit, preferably within 7 days of stopping the investigational product, and perform the procedures indicated for the V7/Early Termination (ET) Visit.

Follow-Up Visit (V8): All subjects who complete the open-label treatment period will be contacted by phone 14 to 19 days after the last dose of investigational product is taken to assess for any new AEs and follow-up on any open AEs. The Investigator may choose to conduct this visit in the clinic and may perform additional assessments if results of any of the V7 evaluations are considered clinically significant.

Table 2. Time and Events Schedule

Study Period:	Screening and Baseline	Open-Label Treatment Period										Follow-up	Unscheduled ^b	
		V1 ^a	V2	V3	V4	V5	V6	V7/ET	V8					
Study Visit Number:	W0	W4	W10	W16	W28	W40	W52	W54						
Study Day: relative to Baseline unless specified	0	28 ± 7	70 ± 7	112 ± 7	196 ± 7	280 ± 7	364 ± 7	14 to 19 days after last dose of IP						
Informed consent	X													
Inclusion and exclusion criteria	X													
Demography, standard medical history	X ^e													
Targeted medical history ^d	X													
Prescription for donepezil ^e	X													
Concomitant medications review	X ^e	X	X	X	X	X	X	X	X	X	X	X	X	X
Urine Drug screen	X											X ^f		X
C-SSRS	X	X	X	X	X	X	X	X	X	X	X	X	X	X
Dispense IP	X	X	X	X	X	X	X	X	X	X	X	X	X	X
Assess IP compliance		X	X	X	X	X	X	X	X	X	X	X	X	X
Physical exam	X			X			X					X		X
Neurological exam	X			X			X					X		X
12-lead ECG	X			X			X					X		X
Vital signs ^g	X	X	X	X	X	X	X	X	X	X	X	X	X	X
Review AEs		X	X	X	X	X	X	X	X	X	X	X	X	X

Study Period:	Screening and Baseline	Open-Label Treatment Period								Follow-up	Unscheduled ^b
		V1 ^a	V2	V3	V4	V5	V6	V7/ET	V8		
Study Visit Number:	W0	W4	W10	W16	W28	W40	W52	W54			
Study Week:											
Study Day: relative to Baseline unless specified	0	28 ± 7	70 ± 7	112 ± 7	196 ± 7	280 ± 7	364 ± 7	14 to 19 days after last dose of IP		UNS UNS UNS	
Serum chemistry, Hematology, Urinalysis	X	X	X	X	X	X	X			X	
Serum or urine pregnancy test ^b	X						X			X	
DS	X				X		X				
EQ-5D	X				X		X				
Telephone Visit								X			

Abbreviations: AE=Adverse event; C-SSRS = Columbia Suicide Severity Rating Scale; DS= Dependence Scale; ECG = electrocardiogram; EQ-5D= EuroQOL 5 dimensions questionnaire; ET = early termination; IP=investigational product; UNS= unscheduled; V = visit; W = week.

Notes:

- The final on-treatment visit, V8, of lead-in study RVT-101-3001 may serve as V1 of this study. If V1 of this study occurs greater than 7 days after V8 of the lead-in study, then all procedures specified for V1 of this study must be repeated and cannot be combined with the procedures performed on V8 of the lead-in study. V1 of this study must occur within 4 weeks of V8 of the lead-in study.
- Unscheduled visits and/or assessments to occur at the discretion of the Investigator.
- Data for demography, standard medical history, and concomitant medications review at Screening will be rolled over from lead-in study RVT-101-3001.
- Targeted medical history will consist only of ongoing medical conditions and open AEs from the lead-in study, if any.
- Clinical prescription for donepezil will be provided by the Investigator or the treating physician.
- For ET visit only.
- Vital signs will include systolic and diastolic blood pressure, pulse rate, respiratory rate, temperature, and body weight at each visit; height will be performed at screening only.
- Pregnancy test required only for women of child-bearing potential.

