6.6.2. Subject Withdrawal Procedures

If a subject is prematurely discontinued from treatment with the investigational product, the investigator must make every effort to perform the evaluations scheduled for the Early Termination Visit ([Table 2](#)). In the case where the subject permanently discontinues investigational product between scheduled clinic visits, he/she should be recalled to the clinic as soon as possible and preferably within 7 days of stopping the investigational product for the Early Termination Visit.

If a subject is lost to follow-up, every effort must be made by study center personnel to contact the subject, inquire about the reason for discontinuation, and follow up with any unresolved AEs/SAEs. A minimum of 3 attempts at contact should be made with 1 contact being by certified letter. All measures taken to contact the subject and information received during those attempts must be documented.

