Collection of AEs and SAEs will begin at the time a subject signs informed consent and continues until the follow-up visit. SAEs that are spontaneously reported by the subject or subject representative or discovered by the investigator or designee after the follow-up visit and up to 30 days after the last dose of investigational product must be collected and reported.

All SAEs will be recorded and reported to Worldwide Clinical Trials or Axovant Sciences within 24 hours of the investigator becoming aware of the SAE according to Section 8.2.1.1.7.

Investigators are not obligated to actively seek AEs or SAEs in former study subjects. However, if the investigator learns of any SAE, including a death, at any time after a subject has been discharged from the study, and he/she considers the event reasonably related to the investigational product or study participation, the investigator must promptly notify the sponsor or sponsor representative.

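### Section 8.1 gives the post-treatment adverse-event call to completers only, so a site following it would schedule no question about new events after an early stopper's termination visit

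*Combined protocol and SAP*

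**What the plan says.** **Completers.** Section 8.1 describes the follow-up visit (V8) as follows: "All subjects who complete the open-label treatment period will be contacted by phone 14 to 19 days after the last dose". Its stated purpose is to pick up new AEs and follow those still open.

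**Early stoppers.** The preceding paragraph of 8.1 deals with them separately. They are "required to attend a safety clinic visit, preferably within 7 days of stopping the investigational product", with the V7/ET procedures. Section 6.6.2, on withdrawal procedures, says that a subject who stops between clinic visits "he/she should be recalled to the clinic as soon as possible and preferably within 7 days of stopping the investigational product". Neither place mentions V8 for this group.

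**AE collection.** Section 8.2.1.1.3 states: "Collection of AEs and SAEs will begin at the time a subject signs informed consent and continues until the follow-up visit". It has no completer limit. SAEs reported spontaneously or discovered "after the follow-up visit and up to 30 days after the last dose of investigational product must be collected and reported". The same section adds: "Investigators are not obligated to actively seek AEs or SAEs in former study subjects".

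**Withdrawal.** Section 6.6.1 treats permanent discontinuation of drug as withdrawal from the study. It also says that AE information goes on being gathered under the normal procedures in subjects who have stopped.

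**Schedule.** Table 2 places V8 after the shared V7/ET column and times it "14 to 19 days after last dose of IP". Section 8 says that "adherence to the study design requirements, including those specified in the Time and Events Table, are essential and required for study conduct".

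**The concern.** Long-term safety and tolerability is the primary objective. The V8 call is the only scheduled point after treatment at which a subject is asked about new AEs. If it goes to completers alone, the subjects left out are those who stopped early, including those who stopped because of an AE.

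The AE collection rule also loses its end point for them: collection runs to a visit that 8.1 does not schedule. About 185 centers are planned, so sites may settle the question differently. A non-serious event that nobody asks about is unlikely to be recovered later.

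Section 10.4.2.1 summarizes Follow-up Period AEs separately. Sections 10.3.1 and 10.4.2 base the safety analyses on everyone who took at least one dose. Early stoppers would therefore probably count in that summary, whether or not anyone asked them about AEs after ET.

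**Working it through.** The plan gives no figure to reproduce. The check is a comparison of the text, followed by day counts.

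**1. What each section implies for an early stopper**

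| Section | What it implies |
|---|---|
| 8.1, V8 paragraph | Names completers only |
| 8.1, open-label paragraph, and 6.6.2 | ET visit; no later contact given |
| 8.2.1.1.3 | AEs collected to the follow-up visit, for any subject |
| 6.6.1 | AE collection continues after drug is stopped; no contact or end date |
| Table 2 | V8 timed from last dose; silent on early stoppers |

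The mismatch with 8.2.1.1.3 is direct, because that section relies on a visit that 8.1 gives only to completers. Section 6.6.1 shows that collection is meant to continue, but the normal procedures it refers to lead back to 8.2.1.1.3 and the same visit. Table 2 differs from 8.1 only by implication.

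**2. Solicited days lost per early stopper at a site following 8.1**

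Inputs: V8 on day 14 to 19 after last dose (8.1, Table 2); ET preferably by day 7 (8.1, 6.6.2).

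Days lost = V8 day − ET day, and zero once ET is on day 14 or later, because ET then falls in or after the V8 window.

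| ET day after last dose | To day 14 | To day 19 |
|---|---|---|
| 0 | 14 − 0 = 14 | 19 − 0 = 19 |
| 7 | 14 − 7 = 7 | 19 − 7 = 12 |
| 10 | 14 − 10 = 4 | 19 − 10 = 9 |
| 13 | 14 − 13 = 1 | 19 − 13 = 6 |
| 14 or later | 0 | 0 |

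With ET on day 7, the subject keeps 7/14 = 50% to 7/19 = 37% of a completer's solicited window. The ET timing is a preference, so a prompt visit widens the gap and a late one narrows it.

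**3. What other provisions cover**

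- AEs already reported are followed to resolution or stabilization (8.2.1.1.6), and clinically significant laboratory values are repeated (8.2.1.6). The questions suggested in 8.2.1.1.5 could bring out new events at those contacts, but at no fixed date.
- A spontaneously reported tolerability problem leads to an unscheduled visit (8.1).
- SAEs are collected to day 30, but only if reported or discovered (8.2.1.1.3).
- The three contact attempts in 6.6.2 are for subjects lost to follow-up.

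None of these schedules a question about new non-serious AEs for an early stopper who has no open AE at ET.

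**4. Number of subjects**

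The documents give an enrollment ceiling of 1150 but no discontinuation rate, no distribution of ET timing and no indication of how many sites would follow 8.1. The count cannot be computed.

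**The case against.** The strongest reply is that the protocol does not intend AE collection to stop at withdrawal. Section 6.6.1 says so for this very group, and read with 8.2.1.1.3 it suggests that a follow-up contact is expected. The sentence about former study subjects sits beside a rule for events learned of after discharge from the study, so it need not cancel the collection period set earlier in the same section. This stands as evidence of intent. It does not supply a date or a contact, and a site can still point to 8.1, 6.6.2 and the withdrawal definition for not calling.

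A reader might infer that 8.1 flatly contradicts Table 2. The documents do not support that. The table names ET where it means it, in the V7/ET column heading and in a note on the drug screen, while the next column is headed only V8 and labelled week 54. That is compatible with a completers-only visit. Section 8 makes the table binding but does not rank it above the text of 8.1. Nor do the 2-week follow-up period in 5.1 or the contraception end point in criterion 3b settle who receives V8.

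The claim about the analysis is also partly inference: the documents define neither the Follow-up Period nor its denominator.

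**Conclusion.** The point holds as an internal inconsistency with a limited effect on data collection. Section 8.1 names only completers for V8, and the sections on early stoppers give them only ET. That does not fit the AE collection rule in 8.2.1.1.3 or the continued collection in 6.6.1.

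At a site following 8.1, the loss per early stopper is 7 to 12 solicited off-drug days with ET on day 7, up to 14 to 19 days with ET on day 0, and none from day 14. It concerns mainly new-onset non-serious AEs in early stoppers with no open AE at ET. On-treatment AEs, AEs reported at ET and discontinuations due to AEs are unaffected, and SAEs are still collected passively to day 30.

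Two larger conclusions are tempting. One is a figure for subjects affected or AEs missed; it would rest wholly on assumed rates. The other is a biased comparison; the analysis is descriptive and tests no hypothesis, so the consequence is incomplete ascertainment in a subset. Severity is minor to moderate.

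**What to change.** Reconcile 6.6.1, 6.6.2, 8.1, Table 2 and 8.2.1.1.3:

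1. Reword the V8 sentence in 8.1 to cover every subject who took at least one open-label dose, completers and early terminations alike, using the existing phone window of 14 to 19 days after last dose. Except those who have died, are lost to follow-up or have withdrawn consent to contact.
2. Add a matching note to the V8 column of Table 2.
3. Add cross-references to it in 6.6.1, 6.6.2 and 8.2.1.1.3, so that the end of AE collection is defined for early stoppers.

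An ET visit falling in or after the window could serve as this contact. That is an optional convenience not found in the documents, and the sponsor would need to confirm it.

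The cost is one reworded sentence, one table note, three cross-references and, with that option, one phone call per early stopper whose ET visit falls before day 14. No new assessment is added and the analysis population is unchanged.
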